#### ***1.4. Technique of MDI administration through the ventilator circuit***

The technique of MDI administration was based on that reported by Dhand and Guntur [15].

Airway secretions were sucked out before drug administration. The heat moisture exchanger was removed, but the humidifier was not. After shaking and warming the MDI to hand temperature, the canister was connected to an AeroChamber® HC MV spacer (Trudell Medical International, London, Canada) and placed in the inspiratory limb of the ventilator circuit 15 cm away from the endotracheal tube. Actuation was synchronized with the initiation of inspiration. Each actuation was performed with an interval of at least 15 s.

#### ***1.5. Personal target $R_{aw}$ determination***

The target  $R_{aw}$  of each patient was determined within 72 h after their admission to the intensive care unit. After confirming that no inhaled bronchodilator has been administered in the preceding 2 h (for fenoterol) or 12 h (for salmeterol/fluticasone), four puffs of fenoterol MDI (100 µg/puff, Berotec®; Boehringer Ingelheim, Ingelheim, Germany) were administered, followed by 8 puffs after 15 minutes, and then 16 puffs after another 15-minute interval. These intensive doses were intended to produce near maximum bronchodilation. Fifteen minutes after these 28 puffs of bronchodilators, we measured  $R_{aw}$ . This  $R_{aw}$  value was possibly the lowest achievable, and was assigned as the patient's personal target  $R_{aw}$  [16]. This personal target  $R_{aw}$  served as the standard (or baseline) to judge responsiveness to subsequent bronchodilator doses.

### **1.6. *Bronchodilator delivery schedule***

All patients in both the personalized-dosing and fixed-dosing groups routinely received four puffs of 25 µg salmeterol/250 µg fluticasone (Seretide® Evohaler® 250; GlaxoSmithKline Inc. Evreux, France) every 12 h until the discontinuation of ventilation. Each patient also routinely received one vial of ipratropium bromide 0.5 mg and salbutamol sulfate 2.5 mg (Combivent®; Boehringer Ingelheim, Ingelheim, Germany) every 6 h, and an injection of intravenous methylprednisolone 40 mg every 8 h for the first 3 days. The use of short-acting bronchodilators on an as-needed basis was not restricted. Based on the  $R_{aw}$  data determined every 8 h, the personalized-dosing group received an additional four puffs of 25 µg salmeterol/250 µg fluticasone plus four puffs of fenoterol (0.1 mg/puff) if the  $R_{aw}$  value was higher than the personal target  $R_{aw}$  (once it coincided with the regular dosing period of salmeterol/fluticasone, only fenoterol was added). No extra doses were

given to the fixed-dosing (control) group of patients regardless of their  $R_{aw}$  value. The bronchodilator delivery schedules are summarized in Fig. 1.

### **1.7. Outcome measurements**

The primary outcome was the deviation of  $R_{aw}$  from the personal target, which was calculated as  $(\text{measured } R_{aw} - \text{target } R_{aw})/\text{target } R_{aw}$ . The evolution of this deviation over the treatment course was also calculated. The secondary outcomes included the number of ventilator-free days from day 1 to day 28, the percentage of breathing without assistance by day 28, the number of episodes of nosocomial pneumonia, the total number of puffs of rescue short-acting bronchodilators, the number of drug-related adverse effects (arrhythmia or hypokalemia with a Naranjo score [17] of more than 4), and the mortality rate at day 180.

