### **1.3. $R_{aw}$ determination**

The enrolled patients were ventilated with either an AVEA® (CareFusion, Yorba Linda, CA, USA), e500 (Newport Medical Instrument Inc. CA, USA), or Evita® 4 (Dräger, Lubeck, Germany) ventilator. When evaluating  $R_{aw}$ , the ventilator settings were transiently switched to volume control

mode with a fixed tidal volume (500 ml) and constant flow (with a rate of 60 L/min). Plateau pressure was measured using a manually controlled end-inspiratory pause lasting for 0.5–1.0 s by qualified respiratory therapists [11]. Consistent with several previous clinical studies [12, 13], our patients were not routinely sedated before  $R_{aw}$  measurements. We made every effort to ensure that the patients were calm during the measurements, including additional sedation if necessary. Each measurement was repeated three times with an interval of at least 1 min, and the average value was calculated.  $R_{aw}$  was calculated using the equation (peak inspiratory pressure – plateau pressure)/flow [14]. After each measurement, the ventilator was set to its usual settings. Thereafter,  $R_{aw}$  was routinely determined every 8 h until the discontinuation of ventilation or the 28th day of the study.

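### The only drug-related safety outcome passes through a causality score in an open-label trial: show all recorded arrhythmia and hypokalaemia by arm beside it and, as a minor point, show triggered short-acting puffs beside the as-needed count

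*Combined protocol and SAP*

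**What the plan says.** All references are to the combined protocol and SAP.

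- **Outcomes (1.7).** Secondary outcomes include "the total number of puffs of rescue short-acting bronchodilators, the number of drug-related adverse effects (arrhythmia or hypokalemia with a" score above 4 on a cited causality instrument). Nosocomial pneumonia and day-180 mortality are also listed, without a causality filter. No count of arrhythmia or hypokalaemia irrespective of score is listed.
- **Blinding (1.1).** The trial is open-label. Nothing says who assigned the causality score or whether that person knew the arm.
- **Treatment difference (1.6).** After each scheduled Raw reading, "the personalized-dosing group received an additional four puffs of 25" µg salmeterol (with fluticasone) "plus four puffs of fenoterol (0.1 mg/puff) if the" reading exceeds the personal target. There is one exception: "once it coincided with the regular dosing period of salmeterol/fluticasone, only fenoterol was added". No such doses were "given to the fixed-dosing (control) group of patients regardless of their" reading.
- **As-needed use (1.6).** "The use of short-acting bronchodilators on an as-needed basis was not restricted". No difference between the arms is stated.
- **Timing (1.3).** Raw "was routinely determined every 8 h until the discontinuation of ventilation" or day 28.
- **Target setting (1.5).** "Fifteen minutes after these 28 puffs of bronchodilators, we measured" the target value. This is described for every patient, without distinction by arm.

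**The concern.** **Safety (main point).** Arrhythmia and hypokalaemia can be counted without judging their cause. The plan counts them only after a causality judgement, and in an open-label trial that judgement may be made by someone who knows which patients had extra beta-agonist. Knowing about the extra doses could push scores up in the personalised arm; confidence in the strategy could push them down. Either way, a difference in the scored count, or the lack of one, cannot be separated from a difference in attribution. No unscored comparison is listed that would let a reader check.

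**Puffs (minor point).** The as-needed count does not measure total short-acting use when one arm also receives fenoterol by protocol. A lower as-needed count in that arm could partly be substitution of triggered puffs for as-needed ones.

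These outcomes bear most directly on what the extra beta-agonist costs the patient, so a reader needs to know what each count can and cannot show.

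**Working it through.** The plan gives no figure for either outcome. Its one power statement (100% with a sample size of 51, section 1.8) concerns the primary outcome, gives no difference or SD, and is not in dispute. I use it only for arm size, reading 51 as the total and taking 26 v 25. Event risks, scoring rates and as-needed rates below are assumptions.

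**1. How attribution moves the safety estimate.** If the true event risk p is equal in both arms, and fractions q1 (personalised) and q0 (fixed) of events score above 4, the scored risk difference is p × (q1 − q0). It should be zero. The last column is the chance of a two-sided Fisher test at 0.05 being significant, by exact enumeration, with patients having an event treated as binomial.

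| p | q1 v q0 | Expected scored patients | Shift | Significant |
|---|---|---|---|---|
| 40% | 50% v 40% | 26×0.4×0.5 = 5.2 v 25×0.4×0.4 = 4.0 | +4 points | 3.9% |
| 40% | 60% v 30% | 6.2 v 3.0 | +12 points | 13.1% |
| 40% | 30% v 60% | 3.1 v 6.0 | −12 points | 17.1% |
| 20% | 60% v 30% | 3.1 v 1.5 | +6 points | 2.9% |

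For comparison, all events at 40% v 40% give 3.8%. A false significant result is therefore uncommon; the effect is mainly on the estimate.

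**2. What the all-event count costs.** Take an assumed drug-caused risk of 25% v 5%. With independent background risk b, all-event risk is b + (1 − b) × drug-caused risk.

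- b = 0: 25% v 5%, Fisher power 41%.
- b = 20%: 0.2 + 0.8×0.25 = 40% v 0.2 + 0.8×0.05 = 24%, power 18%.
- b = 40%: 0.4 + 0.6×0.25 = 55% v 0.4 + 0.6×0.05 = 43%, power 10%.

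The scored count can also lose power. If 80% or 60% of drug-caused events in the personalised arm pass the threshold (25% × 0.8 = 20%, or 25% × 0.6 = 15%, against 5%), power is 22% or 8%. That comparison assumes the control arm loses none. Neither count is better in every case.

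The interval will be wide: 10/26 v 10/25 gives a difference of −2 points, Newcombe 95% CI −27 to +24.

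**3. Triggered short-acting puffs.** Readings per day: 24/8 = 3. At four puffs each, the maximum is 3 × 4 = 12 fenoterol puffs a day in the personalised arm and 0 in the fixed arm. If 25%, 50%, 75% or 100% of readings exceed target, this is 3, 6, 9 or 12 a day.

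If as-needed use is lower in the personalised arm, combined use is equal when the share of readings above target is (fixed as-needed − personalised as-needed)/12, and above that share the direction reverses.

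- 4 v 2 a day: 2/12 = 17%.
- 8 v 4 a day: 4/12 = 33%.
- 12 v 6 a day: 6/12 = 50%.

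The documents do not give the share of readings above target.

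**The case against.** **On safety.** The threshold is a fixed number on a cited instrument, nothing shows that scoring differed by arm, and the milder illustration is significant 3.9% of the time against 3.8% with no difference at all. The 12-point shifts need both a 40% event risk and a twofold gap in attribution. An all-event count is noisier and is not immune either, since in an open-label trial the detection and recording of arrhythmia can also depend on the arm. All of this stands. It limits the size of the claim and what the remedy can deliver. It does not supply the missing check, because a numerical cut-off still rests on a judgement made without described blinding.

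A reader might infer that the safety comparison is biased, or biased in a known direction. The documents do not support that: they show the absence of a safeguard, and the effect could run either way.

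**On rescue puffs.** Section 1.6 treats as-needed use separately from the triggered doses, which it presents as additional. Rescue therefore most naturally means as-needed, and fewer as-needed puffs may be part of the intended effect. This stands. A reader might infer that the rescue outcome is invalid, or that the personalised arm's total is inflated by design because triggered puffs are counted in it. The text does not support either inference, and Fig. 1, which summarises the schedules and is not reproduced in the text reviewed, may settle the term. What remains is that an as-needed count is not total short-acting use.

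**On weight.** These are secondary outcomes, and pneumonia and mortality are compared without a causality filter, so unfiltered harm data are not absent altogether.

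**Conclusion.** The point holds as an inexpensive improvement to secondary outcomes. The primary outcome is unaffected.

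Main point: the only drug-related safety outcome depends on a causality judgement, in an open-label trial with extra beta-agonist in one arm and no described blinding of scorers. The scored count alone cannot separate a true difference from arm-aware attribution. The actual size cannot be derived; under the assumed inputs the estimate moves by 4 to 12 points in either direction, with false significance uncommon. An all-event count would expose a difference in attribution among recorded events. It would not remove arm-aware detection.

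Minor point: the as-needed count is a legitimate outcome, but with 0 to 12 triggered puffs a day in one arm only, it can point the opposite way from combined short-acting use.

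The figures rest on 51 being the total sample and on the assumed risks and rates stated above.

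**What to change.** **Safety.** Report all recorded arrhythmia and hypokalaemia by arm regardless of causality score, with one definition and one observation window for both arms and a confidence interval for the difference. Place this beside the scored count, not in its stead. State whether the scorers knew the allocation.

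**Puffs.** State what rescue covers. Beside the as-needed count, report as-needed plus Raw-triggered short-acting puffs by arm. Give both counts per ventilated day and as totals, because time on the ventilator can differ by arm, over the period of Raw readings and with the 28 target-setting puffs excluded. Do not read a lower as-needed count alone as lower short-acting bronchodilator use. If triggered puffs were not logged, four per reading above target is an approximation that assumes full adherence; say so. As-needed doses not given as puffs would fall outside both counts, which should also be noted.

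**Cost.** A few added descriptive rows and two clarifying statements, with no change to treatment, sample size or existing outcomes. Events must be identified before they can be scored, but nothing says that low-scoring ones were kept, so the all-event table depends on the records. It will include background intensive-care events, and its interval will be wide.

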### **1.8. Statistical analysis**

Data were expressed as number (percentage), mean  $\pm$  standard deviation or median, inter-quartile range (IQR). Each variable was tested for normal distribution using the Kolmogorov-Smirnov test. To compare two continuous variables, we used the Student's *t*-test or the Wilcoxon rank sum test depending on their distribution. For categorical variables, we used the chi-square test or Fisher's exact test as appropriate. A general linear mixed regression model was used to analyze the relative deviation of  $R_{aw}$  over time. This model included fixed effects for the personalized-dosing group, time, and an interaction term of group-by-time, as well as a random intercept and slope. Different durations of stay were considered as the random slope. A *P* value  $<0.05$  was considered to be statistically significant. All statistical analyses were performed using SPSS software (IBM SPSS

Statistics, version 20, IBM Corporation, Chicago, IL, USA). The power of calculating the difference in mean  $R_{aw}$  deviation was 100% with a sample size of 51 and an alpha value of 0.05.

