### **1.2. Patient enrollment**

We enrolled intubated COPD patients who were newly admitted to the intensive care unit of Changhua Christian Hospital (Changhua, Taiwan). A diagnosis of COPD was defined as audible expiratory wheezing or rhonchus or obstructive ventilatory impairment when assessed by spirometry, in addition to a history of smoking or exposure to other forms of toxic stimuli. All of the enrolled patients were endotracheally intubated and had been mechanically ventilated for less than 72 h. The exclusion criteria were: (1) age less than 18 years, (2) confirmed history of asthma, (3) an Acute Physiology and Chronic Health Evaluation II score of more than 35, and (4) comorbid septic shock. The study was approved by the Institutional Review Board of Changhua Christian Hospital (approval No. 120703). Informed consent was obtained from the surrogates of all participants. All of the participants were randomly assigned to the personalized-dosing or fixed-dosing group according to a computer-generated allocation sequence in a block size of four patients.

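### Ventilator-free days, unassisted breathing and 180-day mortality are compared without adjusting for the entry APACHE II score: a cheap gain in efficiency if the score is prognostic

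*Combined protocol and SAP*

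**What the plan says.** Section 1.8 sets the tests by type of variable. For continuous variables: "To compare two continuous variables, we used the Student's *t*-test or the Wilcoxon rank sum test depending on their distribution". For the others: "For categorical variables, we used the chi-square test" or Fisher's exact test. It does not assign a test to each outcome.

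The secondary outcomes in section 1.7 include "the number of ventilator-free days from day 1 to day 28, the percentage of breathing without assistance by day 28", and mortality at day 180. By type, ventilator-free days fall under the t-test or Wilcoxon test. Unassisted breathing and mortality fall under the chi-square or Fisher test.

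The only regression is for airway resistance: "A general linear mixed regression model was used to analyze the relative deviation of" airway resistance from its target. Of its terms the plan says "This model included fixed effects for the personalized-dosing group, time, and an interaction term of group-by-time", with a random intercept and slope. No baseline covariate is named for any outcome.

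Section 1.2 excludes patients with "an Acute Physiology and Chronic Health Evaluation II score of more than 35". It describes allocation in blocks of four and mentions no stratification.

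**The concern.** A score that decides eligibility must be known for each patient before treatment is compared. Here it measures acute severity, which may plausibly predict time on the ventilator and death. The plan uses it neither to stratify the randomisation nor in the analysis. If the score does predict these outcomes, the unadjusted comparisons leave explainable variation in the error term.

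What is at stake is the precision of three patient-centred secondary outcomes in a small trial. The plan's only power statement concerns airway resistance, so nothing in it speaks to the precision of these three. The primary outcome is not affected.

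**Working it through.** **Inputs from the documents.** Sample size 51 and alpha 0.05 (section 1.8); blocks of four (section 1.2). **Assumptions.** 51 is the total, allocation is 1:1 (25 v 26) and alpha is two-sided. The documents give no correlation, standard deviation, event rate or treatment effect for these outcomes, so ranges are shown.

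**The plan's own figure.** Section 1.8 states 100% power for the difference in mean deviation of airway resistance. It cannot be reproduced, because no difference or standard deviation is given. The standardised difference it would need is d = (1.96 + z_power) × √(2/25.5), where √(2/25.5) = 0.280:
- 98% power: (1.96 + 2.054) × 0.280 = 1.12
- 99.5% power: (1.96 + 2.576) × 0.280 = 1.27

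This has no bearing on the three outcomes here.

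**Continuous outcome (ventilator-free days).** Adjusting for one covariate multiplies the variance of the arm difference by (1 − r²)(1 + 1/(N − 4)). With N = 51 the second term is 1 + 1/47 = 1.021. The last column shows what happens to a comparison that has 80% power unadjusted.

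| r | Variance factor | Change | Equivalent N (51/factor) | Power, from 80% |
|---|---|---|---|---|
| 0 | 1.000 × 1.021 = 1.02 | +2% | 49.9 | 79.2% |
| 0.2 | 0.960 × 1.021 = 0.98 | −2% | 52.0 | 80.8% |
| 0.3 | 0.910 × 1.021 = 0.93 | −7% | 54.9 | 82.8% |
| 0.4 | 0.840 × 1.021 = 0.86 | −14% | 59.4 | 85.7% |
| 0.5 | 0.750 × 1.021 = 0.77 | −23% | 66.6 | 89.3% |

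Break-even is where (1 − r²)(48/47) = 1, so r² = 1/48 and r = 0.144.

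Ventilator-free days are bounded and skewed, so the formula was also checked by simulation of a bounded outcome. The variance ratios were 0.98, 0.86 and 0.74 at r of about 0.2, 0.4 and 0.5. Type I error was near 5%, and the cost at r = 0 was about 2%.

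**Binary outcomes (unassisted breathing, mortality).** These were simulated with 25 v 26 patients, no treatment effect, one normally distributed covariate and 8,000 trials per setting. The risk difference was adjusted linearly, as a stand-in for one standardised from logistic regression.

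| AUC of the score | Variance ratio, event rate about 0.5 | Variance ratio, event rate about 0.3 |
|---|---|---|
| 0.60 | 0.99 | 1.00 |
| 0.69 | 0.91 | 0.93 |
| 0.74 | 0.84 | 0.86 |
| 0.79 | 0.78 | 0.80 |

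**If 51 were per arm.** N = 102 and the penalty is 1 + 1/98 = 1.010. The factors at r = 0.3, 0.4 and 0.5 become 0.92, 0.85 and 0.76, so the conclusion is the same.

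**The case against.** **The planned tests are valid.** Under randomisation the unadjusted comparisons keep their type I error and are not biased, and the outcomes are secondary. This stands, and it limits the point to efficiency.

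**The gain depends on an unknown.** A reader might infer that precision is certainly being lost. The documents do not support that: they give no link between APACHE II and any outcome. Excluding scores above 35 and septic shock narrows the range of severity and may weaken the correlation. Below r of about 0.14 there is no gain.

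**Chance imbalance is not a second problem.** The between-arm difference in the score has standard error √(1/25 + 1/26) = 0.280 SD. It therefore exceeds 0.5 SD in 7.4% of trials (0.5/0.280 = 1.785). At r = 0.4 an imbalance of 0.5 SD shifts the outcome by 0.4 × 0.5 = 0.2 SD, about 0.7 of its standard error. The unadjusted test already allows for this in its error rate, so it should not be counted again beside the lost precision.

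**The choice of standard error matters.** With HC3 robust errors part of the gain goes. In simulations of bounded ventilator-free days (25 v 26 patients, 3,000 trials per setting, an assumed effect, Monte Carlo error about 0.9 points), power for t-test, Wilcoxon test and adjusted regression was:
- r about 0.17: 36.6%, 35.4%, 35.0%
- r about 0.33: 32.7%, 31.6%, 32.7%
- r about 0.45: 31.7%, 30.2%, 35.6%

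HC3 was conservative here, with type I error of 3.7 to 4.4%; less conservative forms would show more gain. The form must be named.

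**The estimand changes.** If the Wilcoxon test would have been used, a regression on means answers a different question. For the binary outcomes a conditional odds ratio is also a different quantity, and its standard error need not shrink. Both objections stand and shape the fix.

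**Some links are inferred.** Section 1.8 does not map tests to outcomes. Section 1.2 shows that the score was needed for eligibility, but not exactly when it was scored or that it was kept for analysis.

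**Conclusion.** The point holds as a free or cheap improvement, not as an error. Three secondary outcomes are compared by unadjusted tests although a severity score is needed at entry. The balance of risk favours adjustment: about 2% of variance lost if the score is useless, against 7% to 23% saved for ventilator-free days if r is 0.3 to 0.5. For the risk differences the saving runs from about nothing at AUC 0.60 to 14–16% at AUC 0.74.

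These sizes rest on 51 being the total, on 1:1 allocation and on assumed values of r and AUC. No absolute gain in power can be claimed for this trial, because no effect sizes or event rates are given for these outcomes. Nor do the documents support a claim that the planned comparisons are biased or have inflated type I error.

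**What to change.** In section 1.8, keep the existing tests and add beside them:

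- **Ventilator-free days:** the mean difference from linear regression on arm and continuous APACHE II, with a 95% confidence interval. Use ordinary standard errors or a named small-sample form. State that the estimand is a difference in means and not a rank comparison.
- **Unassisted breathing by day 28 and 180-day mortality:** risk differences standardised from logistic regression on arm and APACHE II, with 95% confidence intervals.
- **Mapping and status:** say which test applies to each outcome. The section is written in the past tense, so if outcome data have already been seen, label the adjusted results as added later.

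The cost is one degree of freedom per model, and a mean-based summary standing beside a possible rank test. No new data are needed, provided the entry scores were kept.

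### The arm difference in mean Raw deviation is not adjusted for the starting deviation, which costs precision but causes no bias, and the time origin of the mixed model is not stated

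*Combined protocol and SAP*

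**What the plan says.** Section 1.7 defines the primary outcome as the relative excess of measured Raw over the patient's target Raw, and adds: "The evolution of this deviation over the treatment course was also calculated". It gives no time point or per-patient summary.

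Section 1.8 offers two routes to an arm comparison. Continuous variables are compared by t-test or Wilcoxon test, with no covariate. The deviation over time goes into a mixed model: "This model included fixed effects for the personalized-dosing group, time, and an interaction term of group-by-time", with a random intercept and slope. On the slope it says only: "Different durations of stay were considered as the random slope". The origin and unit of time are not given. The sample-size sentence begins "The power of calculating the difference in mean" and concerns Raw deviation, with power of 100%, a sample size of 51 and alpha of 0.05.

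Three other sections bear on whether a starting value exists:

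- **Section 1.3:** Raw is read every 8 hours until ventilation ends or day 28.
- **Section 1.6:** after a reading above target, "the personalized-dosing group received an additional four puffs" of one drug plus a second drug. No extra doses were "given to the fixed-dosing (control) group of patients regardless of their" Raw. For both arms, "The use of short-acting bronchodilators on an as-needed basis was not restricted".
- **Section 1.5:** the target is measured after 28 puffs of fenoterol: "These intensive doses were intended to produce near maximum bronchodilation". The section also calls this value a baseline.

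**The concern.** The power statement, and the wording that puts the evolution over time second, suggest that the between-arm difference in mean deviation is the main comparison, although Section 1.8 does not name a test for it. Patients differ in how far above target they start. In an unadjusted comparison of patient means that spread stays in the error term, although a value already on file could remove part of it.

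The target Raw does not do this job. It is the reference and denominator of the outcome and says nothing about how far above it the patient started. The first 8-hourly deviation could do it, because extra doses are given in response to such readings.

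The second issue is interpretation. With a group-by-time term in the model, the group coefficient is the arm difference at time 0. Intubation, ICU admission, randomisation, the target test, study day 1 and the first 8-hourly reading are all possible origins. If time 0 is the first reading, the coefficient describes the arms before any extra dose has acted.

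**Working it through.** **1. The plan's own figure.** The 100% power can be neither reproduced nor refuted, because no difference or SD is given. It can be turned into the standardised difference d that it implies (two-sided 0.05, 1:1 allocation, noncentral t). With 51 patients in total, 98% power needs d of about 1.15 and 99.5% needs about 1.30. With 51 per arm the values are 0.80 and 0.91.

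**2. Effect of the covariate on variance.** Let r be the within-arm correlation between the first deviation and the patient's mean later deviation. The documents do not give r, so it is assumed. With N = 51, ANCOVA multiplies the variance of the arm difference by

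(1 − r²) × (N − 3)/(N − 4) = (1 − r²) × 48/47.

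| r (assumed) | variance factor | SE factor (square root) |
|---|---|---|
| 0.4 | 0.84 × 48/47 = 0.86 | 0.93 |
| 0.6 | 0.64 × 48/47 = 0.65 | 0.81 |
| 0.8 | 0.36 × 48/47 = 0.37 | 0.61 |

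Break-even: (1 − r²) × 48/47 = 1 gives r² = 1/48, so r = 0.144.

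**3. What this means for power.** Normal approximation with 25.5 per arm: unadjusted SE = √(2/25.5) = 0.280 SD, and power = Φ(d/(0.280 × SE factor) − 1.96).

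| d (assumed) | unadjusted | r = 0.4 | r = 0.6 | r = 0.8 |
|---|---|---|---|---|
| 0.5 | 43% | 49% | 60% | 84% |
| 0.8 | 81% | 87% | 94% | 99.7% |
| 1.15 | 98.4% | 99.3% | 99.9% | about 100% |

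At the d that the stated power implies for 51 in total, at most about 2 points remain to be gained.

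**4. Simulation (all inputs assumed).** The set-up was 26 v 25 patients with 8-hourly readings for 7 or 14 days. Intercept/residual SDs were 0.3/0.3, 0.4/0.3 or 0.3/0.4, and slope SD was 0.01, 0.02 or 0.05 per day, giving 18 settings. Both tests used the readings after the first.

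- No effect: rejection 4.6–6.0% for both tests.
- First-to-later correlation 0.38–0.78; variance factor 0.38–0.88, in line with step 2.
- Early effect of −0.3: power 51–92% unadjusted, 67–99.6% adjusted; group-by-time 5–23%.
- Gradual effect reaching −0.4: 27–66% unadjusted, 38–90% adjusted; group-by-time 49–100%.
- The 28 puffs leave 30% of the usual deviation in the first reading: correlation 0.14–0.36, variance factor 0.87–1.00, gain about 0–5 points.
- The 28 puffs leave none of it: variance factor 1.01–1.03, loss of up to 1.5 points.

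**5. Time origin.** A separate simulation assumed equal arms at the first reading and a slope difference of −0.03 per day (100 runs).

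| time 0 | mean group coefficient | significant |
|---|---|---|
| first reading | 0.00 | 7% |
| day 3 | −0.09 | 12% |
| day 7 | −0.21 | 44% |

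The group-by-time coefficient stays at about −0.03 whatever the origin.

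**The case against.** The strongest reply is that nothing here is wrong. Randomisation protects the comparison, so omitting a covariate causes no bias; only precision is affected. For group-by-time the random intercept already absorbs the starting level. Both statements stand.

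Three stronger readings are tempting, and the documents support none of them.

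- **The plan takes the uncentred group coefficient as the treatment effect.** No section says so, and the interaction is in the model to pick up a gradual effect. On its own, the time-0 matter is missing detail.
- **The trial forfeits up to 40 points of power.** The simulated gains of 3–40 points rest on assumed SDs, correlations and effects, with unadjusted power no higher than about 92%. The plan states 100%, and if that holds the gain is about 2 points or less.
- **ANCOVA should replace the mixed model.** For a gradual effect group-by-time is the stronger test, so it should not be demoted.

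The covariate itself is also open to challenge. That the first reading precedes any extra dose is an inference from Section 1.6. The available text does not order randomisation, the target test and the first reading, and Fig. 1, which summarises the schedules, is not shown. The trial is open-label and as-needed drugs are unrestricted, so treatment could differ by arm before that reading. This stands, and it is why a records check is needed.

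Finally, the text is in the past tense, so the analysis may already have been done. That would change the label on the adjusted result, but the result would still be worth showing.

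**Conclusion.** The point holds as a modest, nearly free improvement to consider. It does not identify an error that threatens the result. As written, the plan leaves starting-level variation in the error of the mean comparison and does not state the time origin or which contrast is the treatment effect.

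The likely size is a standard error 7% to 39% smaller for r between 0.4 and 0.8. There is no gain at r of about 0.14, and the loss is up to about 1.5 power points if the 28 puffs erase the starting level. This rests on an assumed r, on 51 being the total split about 1:1, and on the first reading preceding differential treatment. If power is near the stated 100%, the benefit is a narrower confidence interval.

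Adjustment also deals with chance imbalance. At 25 v 26 the SE of the first-deviation gap is √(1/25 + 1/26) = 0.28 SD, so a gap above 0.5 SD occurs in about 7% of trials. Given a gap of 0.5 SD, the unadjusted test rejects a true null in about 11% of trials at r = 0.5 and 16% at r = 0.7. Averaged over all randomisations it keeps its 5%.

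**What to change.** 1. Estimate the arm difference in mean Raw deviation over the readings after the first 8-hourly reading, by ANCOVA on patient means with the first reading's deviation as covariate, or by the mixed model with the same covariate.
2. Report the unadjusted comparison and the planned group-by-time analysis beside it, with group-by-time keeping its planned standing.
3. State the origin and unit of time. Report the treatment effect as a mean difference over the later readings, and do not read it from the uncentred group coefficient.
4. Confirm from the records that the first reading precedes the first extra dose, and tabulate as-needed bronchodilator use before it by arm. If this check fails, or outcomes have already been analysed, present the adjusted result as a labelled sensitivity analysis beside the planned one.

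**Cost.** One variable already collected, a few sentences and a records check; no new data. The first reading leaves the outcome, and patients with only one reading contribute no outcome to the ANCOVA. Patient means count a short stay as much as a long one. In simulations with unequal stays, weighting by number of readings changed power little (early effect: 82–99.5% weighted, 85–99.4% unweighted).
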